## Missing or Partial Death Dates

Missing or partial death dates will be imputed based on the last contact date:

- If the entire date is missing it will be imputed as the day after the date of last contact (see derivation of date of last contact in [Section 5.2.4](#)); or
- If the day or month is missing, death will be imputed to the maximum of the full (non-imputed) day after the date of last contact and the following:
  - Missing day: 1st day of the month and year of death, or
  - Missing day and month: January 1st of the year of death.

## Date of Start of New Anti-cancer Therapy

Incomplete dates for new anti-cancer therapy will be imputed as follows and will be used to determine censoring dates for efficacy analyses. Note that HSCT before the end of the treatment phase or its conditioning regimen(s) are not considered new anti-cancer therapies.

- The end date of new anti-cancer therapy will be included in the imputation for start date of new anti-cancer therapy. If the end data of new anti-cancer therapy is:
  - completely missing then it will be ignored in the imputations below,
  - partially missing with only year available then the imputations below will consider 31DECYYYY as the end date of the new anti-cancer therapy, or
  - partially missing with only month and year available then the imputations below will consider the last day of the month for MMMYYYY as the end date of the new anti-cancer therapy.
- For patients who have not discontinued study treatment at the time of the data cutoff date, last dose of study treatment is set to the data cutoff date in the imputations below.
- If the start date of new anti-cancer therapy is completely or partially missing then the imputed start date of new anti-cancer therapy is:

= 31DECYYYY, if only Year is available and Year < Year of min  
[max (PD/relapse date + 1, last dose of study treatment + 1), end date of new  
anti-cancer therapy]

= Last day of the month, if both Year and Month are available and

Year = Year of min [max (PD/relapse date + 1, last dose of study  
treatment + 1), end date of new anti-cancer therapy]

Month < Month of min [max (PD/relapse date + 1 day, last dose of study treatment + 1 day), end date of new anti-cancer therapy]

= min [max (PD/relapse date + 1, last dose of study treatment + 1), end date of new anti-cancer therapy], for all other cases.

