#### **3.2. Secondary Endpoints**

##### **3.2.1. Efficacy Endpoints**

Secondary efficacy endpoints will be summarized based on data up to initiation of a new anti-cancer drug therapy, if applicable.

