### 3.5. Safety Endpoints

Safety endpoints will be summarized based on the on-treatment period unless otherwise specified.

On-treatment is defined as the time from the first dose of study treatment to last dose prior to HSCT + 28 days and if applicable, from first dose post-HSCT to last dose + 28 days or start of new anti-cancer drug therapy (minus 1 day), whichever occurs first. Note that conditioning regimens for HSCT (regardless of whether glasdegib is resumed after HSCT) are not considered “new anti-cancer drug therapy”. Adverse events occurring on the same day as the first dose of study treatment will be considered to have occurred during the on-treatment period. All other assessments which occur on the same day as the first dose of study treatment will be considered baseline assessments (see [Section 3.4](#) for the definition of baseline).

Safety data collected outside the on-treatment period as described above will be listed but not summarized.

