## Other Missing or Partial Dates

Imputation methods for other partial dates are as follows:

- If the day of the month is missing for a start date used in a calculation, the first day of the month will be used to replace the missing date.
- If both the day and month are missing for a start date, the first day of the year is used.
- For stop dates, the last day of the month, or last day of the year is used if the day or day and month are missing, respectively.
- If the date is completely missing, no imputation will be performed.

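### A new anti-cancer therapy recorded in a later month or year than the reference date is imputed to start before that month or year, so EFS and DoR may be censored too early

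*SAP*

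**What the plan says.** The paragraph on the start of new anti-cancer therapy in SAP 5.3.1 builds a reference date: the earlier of (a) the day after the later of relapse and last dose, and (b) the end date of the new therapy. An end date that is missing altogether drops out: "completely missing then it will be ignored in the imputations below". Three branches follow.

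- Year only: "31DECYYYY, if only Year is available and Year < Year of min", where the minimum is the reference date.
- Year and month, with the recorded year equal to the reference year: last day of the recorded month, if "Month < Month of min [max (PD/relapse date + 1 day, last dose of study treatment + 1 day" and so on, that is, if the month is earlier than the reference month.
- Everything else: "min [max (PD/relapse date + 1, last dose of study treatment + 1), end date of new anti-cancer therapy], for all other cases".

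The paragraph states one use. The imputed dates "will be used to determine censoring dates for efficacy analyses". SAP 3.2.1 applies the cut: "Secondary efficacy endpoints will be summarized based on data up to initiation of a new anti-cancer drug therapy, if applicable". SAP 3.5 also relies on a new-therapy start date, because the on-treatment period ends at last dose plus 28 days or "start of new anti-cancer drug therapy (minus 1 day), whichever occurs first".

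**The concern.** Both branches that use the recorded month or year require it to be earlier than the reference. There is no branch for later, although therapy given after relapse or after stopping study drug would ordinarily start later. SAP 5.3.1 uses the same three-branch layout for the date of last dose. There it is reasonable, because the reference (treatment discontinuation or death) is an upper limit. For new therapy, the day after last dose or relapse is in practice a lower limit, and the same layout discards information that the site did record.

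The imputed date decides which secondary efficacy data count. If it is months too early, valid disease assessments in relapse-free responders are set aside and their EFS or DoR is censored sooner than it should be. If the same date were used in the safety tables, adverse events in the 28 days after last dose could leave the treatment-emergent summaries.

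**Working it through.** No sample size, event count or alpha level depends on this rule, so there is no planned figure to reproduce. The check applies the three branches literally to example dates.

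**Formulas**
- Reference R = min[max(relapse + 1, last dose + 1), end of new therapy], with absent dates ignored.
- If the recorded month or year is later than that of R, branches 1 and 2 do not apply and the imputed start is R.
- Days too early = first day of the recorded month (or 1 January of the recorded year) − R.
- End of the on-treatment window, if SAP 3.5 uses this date = min(last dose + 28, imputed start − 1).

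The dates are illustrative and the end of new therapy is missing throughout. The last two columns give days of safety window after last dose, under the rule and with the start set to the first day of the recorded month or year.

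| Last dose | Relapse | Recorded start | Imputed start | Days too early | Window, rule | Window, first day |
|---|---|---|---|---|---|---|
| 10 Mar 2020 | none | SEP 2020 | 11 Mar 2020 | 174 | 0 | 28 |
| 10 Mar 2020 | none | APR 2020 | 11 Mar 2020 | 21 | 0 | 21 |
| 30 Jun 2020 | none | 2021 | 1 Jul 2020 | 184 | 0 | 28 |
| 10 Mar 2019 | 20 Mar 2019 | JUN 2019 | 21 Mar 2019 | 72 | 10 | 28 |
| 10 Mar 2019 | 9 May 2019 | JUN 2019 | 10 May 2019 | 22 | 28 | 28 |

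A consistent end date does not help. A therapy that began in a later month cannot have ended before it, so the minimum stays at the day after last dose or relapse.

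**How often the branch is reached.** Assume the day is missing, there is no relapse, last dose falls on any day of 2019, and the true start is uniform over 1 to G days after it. The imputed date then precedes the recorded month in 47.7% of combinations for G = 30, 82.5% for G = 90 and 91.3% for G = 180. In the affected combinations the mean error is 10.3, 38.1 and 82.8 days. These shares describe partial dates only. The documents do not say how many there will be.

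**Efficacy consequence.** SAP 3.2.1 censors relapse-free responders at the last disease assessment that verifies their status, so the loss is the assessments made between imputed and true start. After last dose the protocol schedules an end-of-treatment visit within 14 days, site visits with hematology every 3 months for 2 years, and marrow once yearly in remission (Tables 1 and 3). In the first row, a 3-month visit would fall near 10 June 2020. If it counts as a disease assessment, censoring could fall there, 92 days after last dose. Under the rule it falls at the last assessment before the imputed start. If no assessment was made in the gap, the censoring date does not move.

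**Events.** R is at least relapse + 1 whenever therapy follows relapse and the end date is consistent. An enumeration of 585,600 combinations of last dose, relapse and later therapy start found none in which the imputed start fell on or before the relapse.

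**The SAP's other date rules.** For partial death dates, SAP 5.3.1 takes the later of the day after last contact and the first day of the recorded month or year, so the record is respected. For other partial start dates with the day missing, "the first day of the month will be used to replace the missing date". Neither provision is stated to apply to new-therapy dates used for efficacy censoring.

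**The case against.** The case for leaving the rule alone has several parts, and much of it stands as a limit on scope.

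- A reader might infer that the shift of 174 or 184 days is lost EFS or DoR time. It is not. It measures the error in the therapy start date; the censoring date moves only if a disease assessment falls in the gap.
- A reader might infer that relapses are lost. They are not: when the reference is relapse + 1, the EFS or DoR event has already been counted. Treatment failures are dated to randomization and do not move.
- A reader might infer that the 28-day safety window is always cut. The documents do not establish this. The paragraph names efficacy censoring as its only use, SAP 5.3 refers partial dates and the treatment-emergent algorithm to a CDISC Safety Rulebook that is not reproduced, and SAP 5.3.1 has the first-of-month default. Even if this date is used, a relapse 28 or more days after last dose leaves the window unchanged. Deaths within 28 days of last dose are tabulated separately under SAP 6.6.2, and events outside the window are still listed.
- Partial dates might be thought likely because follow-up is by telephone. That applies to long-term follow-up, from year 3; for the first 2 years after last dose, new therapies are collected at 3-monthly site visits.
- OS and its interim boundaries do not use this date, DoR has no between-arm test, EFS lies outside the OS-then-fatigue hierarchy, and the rule is the same in both blinded arms.

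None of this supplies the missing branch. For efficacy censoring the paragraph is specific, and it returns a date that the record rules out.

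**Conclusion.** The rule is wrong as written for a recorded month or year later than that of the reference date: the imputed start precedes the recorded month or year, by 21 to 184 days in the examples. The established effect is confined to relapse-free responders who stopped study drug, later started another therapy and have a partial start date. They lose any disease assessment between the imputed and true start, so EFS and DoR may be censored too early. The documents do not support a claim of lost relapses, a changed OS result or bias between arms.

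The safety effect is conditional on SAP 3.5 using the same date. The window then shrinks to the last-dose day when there is no relapse after last dose, is shortened when relapse falls fewer than 28 days after it, and is otherwise unchanged. The trial-level size cannot be computed, because the number of partial dates is not given. The point rests on a literal reading of the three branches. It is a modest defect, worth correcting because the correction costs so little.

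**What to change.** Add a branch to the new-therapy paragraph in SAP 5.3.1: when the recorded year and month (or the year alone) is later than that of the reference date, impute the first day of the recorded month (or 1 January of the recorded year), not after the end date of the new therapy. Keep the reference date when the recorded month or year equals that of the reference, or when the start date is completely missing. The first three rows of the table would then give 1 September 2020, 1 April 2020 and 1 January 2021.

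In SAP 3.5, state which start date, imputed by which rule, closes the on-treatment window.

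The cost is two sentences in the SAP and a small programming change before database lock. No new data are needed.

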**AE Onset Date:**

The following imputation rules apply if the event is unique for a patient or it is the first of a series of similar events; otherwise, the AE Onset Date will not be imputed:

- If the AE Collection Date is not missing, is less than the Date of First Exposure to Treatment, and is less than the AE Stop Date, then AE Onset Date is set to the Date of AE Collection.
- If the Previous Visit Date is greater than the Date of First Exposure to Treatment and less than the AE Stop Date, the AE Start Date is set to the previous visit date.
- If the Date of First Exposure to Treatment is greater than the previous visit date and less than the AE Stop Date, the AE Onset Date is set to the Date of First Exposure to Treatment.
- Otherwise AE Onset date is set to the AE Stop date.

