### **5.3.1. Missing Dates**

For purposes of data listings, dates will reflect only the information provided by the investigator on the CRF.

If start dates for adverse events or concomitant medications are completely missing a worst case approach will be taken whereby the events will be considered treatment emergent and the medications will be considered concomitant. If only partial information are available (eg, only a month and year or only a year) and the partial information provide sufficient information to indicate the dates are prior to the start of study treatment (eg, month/year less than month/year of first dose) then these will be considered to have started prior to treatment; otherwise a similar worst case approach will apply and these will be considered to have started after treatment.

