**AE Stop Date:**

Ongoing events will have the AE Stop Date set to one of the following values:

- Date of Death, if the patient died and a date of death exists.
- Maximum of (Patient Withdraw date, AE Onset Date, AE Collection Date) if the patient withdrew from the study and a date of withdraw exists.
- Maximum of (AE Onset Date, Subject Summary Collection Date, AE Collection Date) if the Disposition CRF page for the long-term follow-up phase exists but a date of completion/discontinuation does not exist.
- Maximum of (Last Treatment Date, AE Onset Date) if no Disposition CRF page for the long-term follow-up phase exists.

Imputation will only occur if event is unique for the patient, or it is the last of a series of similar events; otherwise the Stop Date will not be imputed. Adverse Events are deemed similar if they have the same verbatim term.

Resolved events will have the AE Stop Date set to the maximum of the AE collection date and the AE Onset date.

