### 6.6.1.3. Adverse Events of Special Interest

These analyses will be performed for treatment emergent AEs of special interest as specified in 3.5.1.

- **Time to AE Onset** (in days) is defined as the time from the date of the first dose to the onset date of the AE, regardless of grade. If a patient has multiple episodes of an AE, the date of the first occurrence is used. Time to AE onset (in days) will be calculated as (AE start date – first dose date +1). Time to onset is calculated for the subgroup of patients who had the specific AE.
- **Time to Grade 3 or 4 AE Onset** (in days) is defined similarly as time to AE onset for Grade 3 or 4 AEs.
- **Duration of AE** (in days) is defined as the cumulative duration across episodes of the AE, regardless of grade, where duration for each episode is the time from the AE start date to the AE end date. For one episode, duration (in days) = AE end date – AE start date + 1. If a patient has multiple episodes of an AE, cumulative duration across all episodes will be used adjusting for any overlap. If a patient has an AE that was ongoing at the time of analysis, the time is censored at the last available on treatment visit date. Duration is calculated for the subgroup of patients who had the specified AE.

Descriptive statistics will be presented for time to AE onset (days), time to Grade 3 or 4 AE onset, and duration of AEs for the subgroup of patients with the AE.

Person-year exposure analyses may also be considered in case of relevant difference in treatment duration between treatment arms.

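### SAP 5.3.1: the AE onset rules miss the case where the previous visit is the first-dose day, so some early events with a missing onset date take their stop date as onset

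*SAP*

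**What the plan says.** SAP 5.3.1, under AE Onset Date, first sets the scope: "The following imputation rules apply if the event is unique for a patient or it is the first of a series of similar events". Any other event keeps a missing onset date. Four branches follow:

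1. An AE collected before first exposure and before its stop date takes its collection date as onset.
2. "If the Previous Visit Date is greater than the Date of First Exposure to Treatment and less than the AE Stop Date": onset is the previous visit date.
3. "If the Date of First Exposure to Treatment is greater than the previous visit date and less than the AE Stop Date": onset is the first-exposure date.
4. "Otherwise AE Onset date is set to the AE Stop date".

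Under AE Stop Date, an ongoing event ends at death if the patient died. Otherwise it ends at one of three maxima, built on the withdrawal date, on the subject-summary collection date, or as "Maximum of (Last Treatment Date, AE Onset Date) if no Disposition CRF page for the long-term follow-up phase exists". A resolved event ends at the later of its collection and onset dates.

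SAP 6.6.1.3 uses these dates for AEs of special interest. Time to onset "is defined as the time from the date of the first dose to the onset date of the AE, regardless of grade", counted with one day added. The duration of an episode is end minus start plus one. An AE still ongoing at the analysis is censored at the last on-treatment visit.

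**The concern.** Branches 2 and 3 mirror each other and both are strict, so a previous visit on the first-exposure date satisfies neither. That is not a rare coincidence. SAP 3.4 takes first dose as the earliest non-zero dose of any study drug, and Protocol 6.2 has Day 1 assessments done before dosing on that day. The Day 1 visit and first exposure therefore normally share a date. The next scheduled visit is Day 7 (±3 days) in the non-intensive study (Protocol Table 3) and about a week after Day 1 in the intensive study (Protocol Table 1). A missing-onset event first recorded there has Day 1 as its previous visit.

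The rest of the rule suggests that Day 1 was intended, since a previous visit at screening gives onset on Day 1. As written, an event that must have begun in about the first week is dated at its end. That affects time to onset and duration for the earliest AEs of special interest. It may also affect the SAP 6.6.1 tables that separate events before, during and after HSCT: an early ongoing event in a patient who resumed blinded therapy could be counted after transplant instead of before.

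**Working it through.** The SAP gives no figure on this point to reproduce; the check is of date logic.

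**Equality.** Let F be first exposure (Day 1), P the previous visit, S the stop date and C the collection date. Take P = F = 1, C = 8 and S > 1.

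- Branch 1 needs C < F: 8 < 1 is false.
- Branch 2 needs P > F: 1 > 1 is false.
- Branch 3 needs F > P: 1 > 1 is false.
- Branch 4 applies: onset = S.

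**Is any other day caught?** The four branches were run in order for post-treatment collection, over previous-visit days −28 to 59 and stop days 2 to 399. Among cases with the stop date after both first dose and previous visit, only P = Day 1 reached branch 4. Two neighbouring cases behave sensibly: a previous visit at screening gives onset Day 1 (branch 3), and a previous visit on Day 7 gives onset Day 7 (branch 2).

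**Size.** The Day 8 collection date and the stop days below are illustrative assumptions, except that 10.4 months is the planning median for the non-intensive control arm (10.4 × 30.4375 = 316.6, taken as Day 317) and 168 days is six 28-day cycles. True onset lies between Day 1 and Day 8, so the error lies between S − 8 and S − 1 days. For the ongoing rows the stop date is taken as imputed first.

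| Event recorded on Day 8, previous visit Day 1 | Onset as written | Days late | Onset with an inclusive branch 2 |
|---|---|---|---|
| Resolved, stop Day 8 | Day 8 | 0 to 7 | Day 1 |
| Resolved, stop Day 20 | Day 20 | 12 to 19 | Day 1 |
| Ongoing, last dose Day 28 | Day 28 | 20 to 27 | Day 1 |
| Ongoing, last dose Day 168 | Day 168 | 160 to 167 | Day 1 |
| Ongoing, death at 10.4 months | Day 317 | 309 to 316 | Day 1 |

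In the last four rows the imputed onset falls after the day on which the event was recorded. With the inclusive branch, onset is at most 8 − 1 = 7 days early.

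**Duration.** For the resolved event stopping on Day 20, the formula gives 20 − 20 + 1 = 1 day as written, against 20 − 1 + 1 = 20 days with the change. For ongoing events the result depends on which end date is used. With the imputed stop date it is 1 day. With censoring at the last on-treatment visit it can be negative: if that visit were Day 1 of Cycle 6 (5 × 28 + 1 = Day 141) and last dose were Day 168, the formula gives 141 − 168 + 1 = −26 days.

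**The case against.** Several stronger readings are tempting, and the documents do not support them.

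- *Late onsets drop events from the treatment-emergent tables.* A reader might infer this from the 28-day on-treatment window in SAP 3.5. But SAP 5.3.1 opens by classing events with a completely missing start date as treatment emergent. It extends the same worst-case approach to dates where "If only partial information are available (eg, only a month and year or only a year" and so on, unless what is known places the start before treatment. Incidence does not rest on the imputed onset.
- *The partial-date rule and the onset branches class the same AE differently.* The first decides whether an event preceded treatment; the second supplies a date. The text yields no clear case of conflicting classification.
- *Onset is often months late.* For resolved events the error is limited by the stop or collection date. Months arise only for ongoing events with a late stop date, and the documents give no count of these.
- *Every ongoing event is given a one-day duration.* SAP 6.6.1.3 censors events ongoing at analysis at the last on-treatment visit, so one day is not reliably what the plan produces.

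Two further objections carry some weight. The order of imputation is unstated: three of the four stop rules for ongoing events use the onset date, while every onset branch except the first assigns or tests a date that needs the stop date as well, and the first also tests it. The large errors assume that the stop date is filled first. Also, SAP 5.3 says that a CDISC Safety Rulebook will be followed for missing dates. Its content is not available here and might cover equality. It cannot be assumed to override an explicit algorithm in the SAP, and if it differs, the SAP should say which governs.

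**Conclusion.** The gap is real and can be shown from the text alone, but it is minor. It affects a unique or first-in-series AE with a missing onset date, first recorded at the visit straight after Day 1. In the worked cases a resolved event is dated at most 7 or 19 days late. An ongoing event may be dated weeks to months late if its stop date is imputed first.

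The consequence is confined to descriptive time to onset and duration of AEs of special interest, and possibly the HSCT-period tables. No efficacy endpoint, hypothesis test or stopping boundary is touched. The conclusion assumes that the previous visit, which the SAP does not define, means the visit before the AE was collected, with no unscheduled visit in between. How many AEs will lack an onset date cannot be known from the documents; the number is probably small.

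**What to change.** In the AE Onset Date rules:

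1. In the previous-visit branch, change *greater than* to *greater than or equal to* the date of first exposure. Onset then becomes Day 1 in every affected case with a stop date after Day 1. Cases with a previous visit before or after Day 1 keep their present result under this change.
2. In the fallback, set onset to the earlier of the AE stop date and the AE collection date (the stop date alone if no collection date exists), so that the fallback never dates an event after it was recorded.

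It would help to add one sentence each to define the previous visit and to state whether stop or onset is imputed first. The cost is a short SAP wording change and a small edit to the date-derivation program before database release; no new data are needed.
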